4.1. Inclusion criteria

- Adult (>18 years, regardless of gender, race or ethnicity).
- To be implanted with intracranial depth or grid/strip electrodes for surgical evaluation.
- Patient was not shown, during phase I seizure monitoring, to exhibit abnormal EEG activity in response to photic stimulation, and is not clinically suspected to be susceptible to photic-induced seizures.
- Patient has no pre-existing diagnosis of autism.
- Patient is not considered at risk for psychogenic nonepileptic seizures (PNES) triggered by sensory stimulation.
- Fluent in English.
- Able to understand an informed consent (comprehend potential risks and benefits).
- Give written and verbal informed consent to all experiments patient would participate in.

4.2. Exclusion criteria

Failure to meet any one inclusion criteria.

4.3. Informed consent

To avoid any sense of coercion of the potential participant by the patient's physician, another investigator or the study coordinator will be the recruiter for the study. The physician will refer a patient who satisfies the inclusion criteria to the recruiter, but he will not be the recruiter for the study. All recruited patients engage in a detailed informed consent before the study, prior to becoming an official participant. The below actions surmise the detailed informed consent by the recruiter:

- The recruiter fully explains the purpose, procedures, risks, and benefits of participation, efforts to safeguard all confidential data, their freedom to opt out of the study at any time without affecting any current or future care that they may receive, and other terms, all of which are on a form (see eIRB attachment).
- After the recruiter concludes the explanation, a patient who is interested in becoming a participant in the study signs an informed consent form (see eIRB attachment) to acknowledge their participation and understanding of terms for the study.
- A copy of the consent form is given to the patient and the original document is placed in their medical record.
- A person who declines to participate in the study will sign nothing, but be reminded that their decision will not affect their clinical care.

The consent process may be done in person at Emory University Hospital or remotely. In the case of remote consent:

- The subject will be contacted (by an investigator other than patient's physician, or a study coordinator) via phone or other form of electronic communication such as Zoom, to gage interest in the study. If the subject is interested in participating, a copy of the consent form will be provided to the patient so he/she can read over it, either via encrypted email or an intermediary person, such as the patient's physician or another member of the study team.
- The subject will then be contacted again via phone or other form of electronic communication such as Zoom, to walk the patient through the consent form, answer any questions, and further gage interest in the study. If needed, the patient will be provided further time to read over the consent form.
- If the subject agrees to participate, he/she will sign the consent form, and either:
 - Email (via encrypted email) or fax a scanned copy, or email a picture, of the signed page of the consent form.
 - Give the signed consent form to a study member.
- The investigator (not the patient's physician) or study coordinator who carried out the consent discussion will then sign the consent form, to complete the consent process.

4.4. Study timelines

We anticipate that each recruited subject will participate in one or more experimental sessions (if and when the patient is agreeable to do so) during the 2-4 weeks while they are in the hospital being investigated by the clinical team for intracranial seizure localization.

4.5. Withdrawal from study

Any includable patient who declines to enroll in the study or included patient who wishes to withdraw from the study after consenting to participate is allowed to withdraw from the study with no effect on the clinical care for the patient. Our previous experience with over 100 patients who undergo presurgical evaluation with implanted electrodes demonstrates that the vast majority of patients accept participation in research studies while they are being monitored for seizures.

The researchers will stop a subject's participation in the study without their consent for any reason, especially if they believe it is in their best interest or if they were to object to any future changes that may be made in the study plan.

5. STATISTICAL ANALYSIS

For objectives 1 and 2, we will perform analyses similar to the ones used in Martorell et al.'s study². We will perform a power spectral density analysis of LFP signal in function of frequency and modality (visual, auditory or audiovisual) of the sensory flicker stimulus, using multi-taper methods. Comparisons will be drawn between the mean power spectral density under a given condition and control (random sensory flicker or no flicker) condition, using the Wilcoxon rank-sum test with Bonferroni correction for multiple comparisons. To analyze firing rate modulation of single units to sensory flicker, we will produce a histogram of each single unit's firing rate

aligned to the onset of light and/or sound stimulus. Moreover, we will analyze how strongly the firing rate of single units is phase-locked to the stimulus being played, by calculating and comparing the vector strength of their firing rate modulation under different conditions, using the Kolmogorov-Smirnov test.

For objective 3, we will use similar methods as mentioned above, and compare the effect size of LFP entrainment and firing rate modulation in different brain regions, in function of various sensory flicker parameters (i.e. frequency and modality).

For objective 4, we will do within-subject comparison of the rate of interictal epileptiform discharges during various stimulation and/or baseline conditions. If normally distributed we will use t-test to compare the conditions, otherwise we will use repeated-measures ANOVA.

For objective 5, memory performance will be compared with a repeated-measures ANOVA across the different conditions (e.g. for example, 5.5Hz or 40Hz audiovisual flicker vs. random audiovisual flicker). For one of the memory experiments, performance in the case of random flicker will serve as the baseline from which we will infer any improvement or impairment in memory performance.

All neural data analyses will be performed in Python and/or MATLAB.

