1.3.1. Primary Outcome Measures

The primary outcome measure is the effect of sensory **flicker** exposure on local field potential (LFP): comparing mean power spectral density at the frequency of flicker being presented between flicker and baseline periods. [Time Frame: Up to 6 weeks]

Power spectral density of the LFP will be measured across stimulus frequencies and modalities of sensory flicker stimuli in visual areas, auditory areas, hippocampus and prefrontal cortex. The mean power spectral density measured in dB at the frequency of flicker being presented will be compared between flicker stimulation and no-stimulation baseline periods.

1.3.2 Secondary Outcome Measures:

The secondary outcome measure is the effect of sensory flicker on interictal epileptiform discharges (IEDs), which represent pathological activity often observed in epilepsy [Time Frame: Up to 6 weeks]

The effect of the sensory flicker will be evaluated by the comparison of the whole-brain rate of IEDs between sensory flicker stimulation and baseline (no stimulation).

1.3.3 Exploratory Outcome Measures:

- 1) To study whether sensory flicker exposure can entrain LFPs and modulate single neuron activity in higher cognitive areas such as the hippocampus and prefrontal cortex.
- 2) To identify the modality and frequency of flicker to which given brain regions are most efficiently modulated at the LFP and the single unit levels.
- 3) To identify potential effects of audiovisual flicker on various cognitive processes through a behavioral task.
 - a. If there are effects, to identify their electrophysiological correlates (such as changes in sharp-wave ripples' rate).
- 4) To compare the effects of sensory flicker modulation to direct electrical modulation of various neural circuits within individual subjects.

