2.2.1. Electrode placement

Electrodes are implanted stereotactically to help localize the seizure focus. As a standard means to increase accuracy, the surgery is guided by contrasted MR images, with post-operative reimaging for confirmation. The electrodes (Adtech, PMT or DIXI) have contacts for electrophysiological (LFP) recording and for stimulation. An electrode may include macroelectrode contacts only or macro- and micro electrode contacts. All electrodes are FDA-approved equipment for recording intracranial EEG during presurgical evaluation. Number and

locations of electrodes will be placed on purely clinical grounds, but may be used thereafter for research purposes in consenting subjects under the supervision of the director of the epilepsy monitoring unit (a neurologist) and the supervising neurosurgeon.

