4. PARTICIPANT RECRUITMENT

We aim to include, across all experiments, about 100 adult patients (most patients will only participate in one or a few of the experiments) with pharmaco-resistant epilepsy in whom intracranial depth or grid/strip electrodes are implanted in order to determine the area of seizure onset for possible surgical resection. We anticipate having access to an adequate sample size to attain significant preliminary data in one year. Between two neurosurgeons, our center implants >50 epilepsy patients per year for intracranial monitoring. Approximately 90% of these patients will meet all inclusion criteria.

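### The primary LFP outcome is asked by brain region, apparently within patients, but the only LFP power test named is for independent samples, with no stated unit, pairing or rule for combining contacts

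*Combined protocol and SAP*

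**What the plan says.** Section 1.3.1 says that power spectral density will be measured "across stimulus frequencies and modalities of sensory flicker stimuli in visual areas, auditory areas, hippocampus and prefrontal cortex", and that its mean in dB at the flicker frequency "will be compared between flicker stimulation and no-stimulation baseline periods".

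Section 5, under objectives 1 and 2, describes a multi-taper analysis by flicker frequency and modality. Each condition is compared with a "control (random sensory flicker or no flicker) condition", "using the Wilcoxon rank-sum test with Bonferroni correction for multiple comparisons". No other test for LFP power is named. Objective 3 refers back to similar methods, to "compare the effect size of LFP entrainment and firing rate modulation in different brain regions", without naming a test or model. For the secondary outcome the same section is explicit: "we will do within-subject comparison of the rate of interictal epileptiform discharges". Memory performance gets a repeated-measures ANOVA.

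On data structure, Section 2.2.3 expects tens to hundreds of contacts per patient, and Section 2.2.4 describes sequences of trials. Section 2.2.1 says that "locations of electrodes will be placed on purely clinical grounds". Section 4 aims for about 100 patients across all experiments, but "most patients will only participate in one or a few of the experiments". The documents give no alpha, SD, within-patient correlation, effect size, number of patients per region or number of tests.

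**The concern.** The rank-sum test assumes two independent samples. Flicker and baseline periods from the same patient are correlated, and contacts and trials are clustered within patients. Section 5 does not say whether the observation is a trial, a contact or a patient, or how contacts become a regional value. Three quite different analyses therefore fit the same sentence, and the choice could be made after the data are seen. Bonferroni corrects for the number of tests. It does not correct for ignored pairing or clustering.

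Two links are inferences. Section 1.3.1 does not use the words within patients; the pairing follows from the absence of any described control group. The rank-sum sentence is matched to the primary outcome by content, because the objective numbers in Section 5 do not follow Section 1.3 and its control also allows random flicker.

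**Working it through.** There is no planned power or error figure to reproduce. All inputs below are assumed: two-sided tests at nominal 5%, normal data, simulation error at most about 1.3 percentage points.

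**Reading A: one mean per patient and condition.** SD 5 dB in each condition, correlation r, N patients, 20,000 runs. The true variance of the mean difference is 2 x 25 x (1 - r)/N; an independent-samples test assumes 2 x 25/N. Its size is therefore about P(|Z| > 1.96/√(1 - r)). At r = 0.3, 0.5 and 0.8 the cut-offs are 2.34, 2.77 and 4.38, giving 1.9%, 0.6% and under 0.1%. Simulated rank-sum sizes are 2%, 0.7% and under 0.1%.

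Power, rank-sum versus signed-rank:

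| Shift, N, alpha | r = 0.3 | r = 0.5 | r = 0.8 |
|---|---|---|---|
| 2 dB, 20, 0.05 | 19 vs 29% | 16 vs 38% | 9 vs 75% |
| 2 dB, 40, 0.05 | 39 vs 53% | 38 vs 68% | 33 vs 97% |
| 5 dB, 20, 0.05/24 | 39 vs 57% | 38 vs 77% | 37 vs 100% |

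At r = 0 nothing is lost (2 dB, N = 20: 22 vs 21%). For 5 dB at an uncorrected 0.05 the loss is small (89-98% vs 94-100%). The 24 tests are an assumed 4 regions x 3 modalities x 2 frequencies.

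**Reading B: trials pooled over patients.** 20 patients x 30 trials per condition, trial SD 3 dB, patient SD a, independent patient-by-period SD b in each condition, no average effect, 6,000 runs. The ratio of true to assumed variance is

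(30b² + 9)/(a² + b² + 9).

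For a = 0, b = 1 it is 39/10 = 3.9, so size is about P(|Z| > 1.96/√3.9 = 0.99) = 32%. For a = 5, b = 0 it is 9/34 = 0.26, so size is about P(|Z| > 3.81), under 0.1%. The test is liberal when 29b² > a², that is, when b exceeds 0.56 dB at a = 3 or 0.93 dB at a = 5. Simulated rank-sum size:

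| Patient SD a | b = 0 | b = 0.5 | b = 1 | b = 2 |
|---|---|---|---|---|
| 0 dB | 5% | 14% | 32% | 52% |
| 3 dB | 0.8% | 5% | 19% | 42% |
| 5 dB | <0.1% | 0.8% | 8% | 30% |

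Signed-rank on patient differences stays at 4-5% throughout.

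Pooled contacts behave in the same way. With 20 or 50 patients, 5 or 20 contacts each and an intraclass correlation of change from 0.05 to 0.5, rank-sum size runs from 0.1% to 54%. Pairing alone is no cure: signed-rank on pooled contacts gives 6% to 55%. Signed-rank on patient means gives 4% to 6%.

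**Reading C: trials within one contact.** 30 trials per condition, lag-1 autocorrelation 0 to 0.7, 20,000 runs. In random order, size is 5% throughout, so the test is valid. In strict alternation it falls from 5% to 0%. With one block per condition it rises from 5% to 39%; the documents do not say that this layout is used. Contact-level results still need combining. If a region counted as positive when any one contact reached an uncorrected 0.05, independent contacts would give 1 - 0.95^20 = 64% for 20 contacts.

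**The case against.** The strongest defence is Reading C. Section 5 does not exclude it, and with randomised trial order the rank-sum test holds its level there. Section 1.3.1 also never states a pooled regional test over patients. On this view the defect is an unstated unit, not a wrong test. That much stands, and a reader might infer too much here: that rank-sum is invalid for this trial, or that the primary analysis inflates false positives. The documents support neither. The unit is open, and the error runs from very conservative to strongly liberal depending on quantities they do not give. A reader might also cite the within-subjects wording in the Abstract as proof of pairing, but it concerns the comparison with electrical stimulation.

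Reading C does not close the gap, because separate contact tests say nothing about a region over patients and no combining rule is given. Nor does the deferral to a cited mouse study. The Figure 2 caption in Section 1.2.1 describes that study's spectra across recording days and at the site with the largest peak. That is a display and does not settle the test unit.

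**Conclusion.** The point holds for the regional reading of the primary outcome. The only LFP power test named is for independent samples, and the plan has no unit, pairing, clustering term or combining rule. On patient means it is conservative whenever the within-patient correlation is positive: at a 2 dB shift and N = 20, power is 19 vs 29% at correlation 0.3 and 9 vs 75% at 0.8. On pooled trials or contacts, size runs from about zero to over 50%. These figures illustrate the spread under assumed inputs; they do not measure the error in this trial. The qualitative conclusion needs no particular value, only that both periods come from the same patients and that a result by region is wanted. This is the sole primary outcome, so the unit and the test should be settled before analysis.

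**What to change.** In Section 5, for the primary comparison and separately for each region, modality and flicker frequency:

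- Compute one value per patient: the mean dB difference, flicker minus no-stimulation baseline, over trials and over all contacts assigned to the region by anatomy and not by response.
- Test these differences across patients with one paired test fixed before the data are seen, either a paired t-test on the patient means or Wilcoxon signed-rank.
- State the number of region x modality x frequency tests in the Bonferroni family, and report the number of patients per region.
- Keep contact-level rank-sum over randomised-order trials as a descriptive map. A mixed model with a patient-level random slope can be a sensitivity analysis, with small-sample degrees of freedom: in a balanced design a z test has size of about 11%, 9% and 6% at N = 6, 8 and 20.

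Modality and frequency must stay separate. If 2 dB is present in two of three modalities and absent in the third, averaging over modalities cuts signed-rank power at N = 20 from about 75% to 41% (difference SD √(2 x 25 x 0.2) = 3.16 dB).

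The cost is SAP wording and little code, with no new data. There are three downsides.

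- Focal responses are diluted. A 2 dB response in only half of a region's contacts (same difference SD) cuts signed-rank power from 75 to 26% at N = 20 and from 97 to 48% at N = 40.
- Regions with few patients have little power. The smallest exact signed-rank p is 2/2^N, so 6, 8, 9, 10 or 11 patients are needed for 1, 4, 12, 24 or 48 tests; for 24, 2/2^10 = 0.00195 against 0.05/24 = 0.00208. A paired t-test has no such floor but assumes roughly normal differences. At N = 8 and 24 tests (difference SD 3.16 dB) its power is about 4% for 2 dB and 48% for 5 dB, where signed-rank has none.
- P-values may become more or less favourable, depending on the unit that had been intended.

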2.2.3. Intracranial electroencephalographic (iEEG) activity

This study analyzes routine diagnostic EEG data that is generated using intracranial electrodes. The number, type, orientation, and size of the iEEG electrodes depend on the anatomy and clinical considerations per patient. Typically, there will be tens to hundreds of electrode contacts arranged as a depth, strip, and/or grid. An electrode may be relatively large (macroelectrode) or very small (microelectrode). Macroelectrode local field potentials (LFPs) consist of 0.1-1000 Hz signals obtained from iEEG contacts placed either within the brain (i.e. recorded from depth electrodes) or on the surface of the brain (i.e. recorded from subdural strip or grid electrodes). These signals will be acquired at 1000-2000 samples per second and 12-bit precision for electronic storage. Both the standard and investigational macroelectrode iEEGs are automatically stored to a 2-Petabyte RAID server that is securely managed by Emory Healthcare Information Services (EHc-IS). The stored data is directly accessed via a password-protected Epilepsy Monitoring Unit EMU data system that is securely managed by EHc-IS. Microelectrodes record signals at a sampling rate of up to 30,000 samples per second and 16-bit precision for electronic storage. These signals are then processed by applying a high-pass filter between 200 and 750 Hz, in order to extract the extracellular action potential waveforms (single unit activity) from neurons located in the vicinity of the recording contact.

2.2.4. Exposure to sensory pulses and flicker.

To expose the patient to sensory flicker and individual pulses sensory stimulation, we will use modified versions of the DAVID device (Mind Alive Inc., <https://mindalive.com/>), a commercially available device, and headphones or earbuds. Versions of the DAVID device were used in a recent study described above¹³ (Figure 4) and in many other human studies¹⁷⁻²⁴. Our device consists of opaque glasses containing LEDs to present light flashes, with or without see-through holes, as well as earbuds or headphones to present sound bursts. Patients will be exposed, for about 10

to 60 minutes at a time, to a sequence of sensory flicker trials each lasting a few seconds to 5 minutes, while their eyes are open or closed. Each trial may include the following modalities and frequencies of flicker:

- Modalities: auditory only, visual only, or audiovisual combined.

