- Frequencies: random, or anywhere from 3Hz to 200Hz.

Additionally, subjects may be exposed to individual pulses of light and/or sound, i.e. around or less than 1 pulse /second, for up to 20 minutes at a time.

For experiments characterizing neural response to sensory flicker, patients may be exposed for about 10 minutes to a single modality and frequency combination, such as 40Hz (gamma-like) audiovisual flicker, 5.5Hz (theta-like) audiovisual flicker, or random audiovisual flicker.

For one of the experiments testing the effects of sensory flicker on memory, patients may be exposed to audiovisual flicker for up to about 36 minutes at a time.

For another experiment, patients may be exposed to audiovisual flicker of a given frequency or random frequency, at modalities of visual only, auditory only, or audiovisual combined, for up to 1h at a time.

For another experiment testing the effects of sensory flicker on memory, patients may be exposed, eyes open, to visual flicker via a strip of LEDs secured to the perimeter of a monitor screen that presents images or words, or via wearing a customized DAVID device with glasses that have view holes; sound stimulus will be again provided via earbuds or headphones. In this experiment, sensory flicker would last for a few seconds at a time.

For other experiments testing the effects of sensory flicker on memory or interictal epileptiform discharges, patients may be exposed, eyes open, to visual and/or auditory flicker, anywhere from 10s to 60 minutes at a time, while performing on a spatial navigation task (see more details below). Visual flicker will be administered via customized DAVID device with glasses that have view holes, and auditory flicker will be administered via earbuds or headphones.

For most to all experiments involving exposure to visual and/or auditory stimuli, there will be an occluded condition. In this occluded condition, the subject will wear a sleeping mask or towel on their eyes (under the LED glasses mentioned above), and commercially available earplugs; in this condition, they will be exposed to similar visual and/or auditory stimuli as in the non-occluded condition. Subjects will be instructed on how to properly wear earplugs by specifying instructions similar to the ones available here: <https://www.cdc.gov/niosh/mining/content/earplug.html>.

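### Section 5 corrects the primary spectral-power comparisons by Bonferroni; Holm gives the same familywise protection and never less power, with a gain that runs from almost nothing to about 11 percentage points

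*Combined protocol and SAP*

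**What the plan says.** Section 5 (Statistical Analysis) sets out the comparison of spectral power: "Comparisons will be drawn between the mean power spectral density under a given condition and control (random sensory flicker or no flicker) condition". The same sentence then names the test and the multiplicity method, which the plan gives as "using the Wilcoxon rank-sum test with Bonferroni correction for multiple comparisons". Section 5 does not call these comparisons primary, but the measure matches the primary outcome in Section 1.3.1. There, power at the presented flicker frequency is to be assessed "across stimulus frequencies and modalities of sensory flicker stimuli in visual areas, auditory areas, hippocampus and prefrontal cortex" and compared with periods without stimulation.

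The factors that could enter the correction are these:

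- **Regions:** four (Section 1.3.1).
- **Modalities:** three. Section 2.2.4 has "Modalities: auditory only, visual only, or audiovisual combined".
- **Frequencies:** an open range. Section 2.2.4 has "Frequencies: random, or anywhere from 3Hz to 200Hz" and names 5.5 Hz and 40 Hz as examples.
- **Control:** only the unstimulated baseline in Section 1.3.1, but "control (random sensory flicker or no flicker) condition" in Section 5.
- **Contacts:** Section 2.2.3 says "Typically, there will be tens to hundreds of electrode contacts arranged as a depth, strip, and/or grid". Neither Section 1.3.1 nor Section 5 says how contacts within a region are combined or tested.

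The plan states no overall alpha, no number of comparisons, no effect size and no power calculation.

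**The concern.** The primary outcome is a set of related comparisons, and more than one of them may be real. In that setting Bonferroni holds every comparison to alpha divided by the full number of tests, even after some null hypotheses have been rejected. Holm relaxes the divisor as rejections accumulate and keeps the same familywise guarantee. At stake is some power for the second and later findings, for example for the hippocampus or prefrontal cortex after a visual or auditory area has already shown a response.

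A secondary matter is that a correction by number of tests needs that number. The plan leaves it open, so the per-test threshold is not fixed before the data are seen. This would be so under Holm as well as under Bonferroni.

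**Working it through.** There is no figure in the plan to reproduce, because alpha, number of tests and power are all unstated.

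**Inputs.** From the documents: 4 regions, 3 modalities, 2 named frequencies. Assumed: overall two-sided alpha 0.05; a real effect of 3 standard errors on a normal scale; independent tests for the power simulation. Holm's error control itself does not need independence.

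**Why Holm cannot lose.** Order the p-values p(1) ≤ … ≤ p(m). Bonferroni rejects when p ≤ α/m. Holm rejects p(j) as long as p(j) ≤ α/(m − j + 1) and all smaller p-values have been rejected. The first Holm threshold is α/m and later ones are larger, so every Bonferroni rejection is also a Holm rejection. With m = 4 the Holm thresholds are 0.05/4 = 0.0125, 0.05/3 = 0.0167, 0.05/2 = 0.025 and 0.05/1 = 0.05. Bonferroni uses 0.0125 four times.

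**Bonferroni power per real effect** = P(Z > z − 3), where z is the two-sided critical value at 0.05/m:

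- m = 4: z = 2.498, so P(Z > −0.502) = 69.2%.
- m = 12 (4 regions × 3 modalities at one frequency): z = 2.865, so P(Z > −0.135) = 55.4%.

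**Holm against Bonferroni.** I simulated 200,000 sets of independent two-sided z-tests per row, with mean 3 for real effects and 0 otherwise. Power is averaged over the real effects.

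| Tests | Real effects | Bonferroni | Holm | Gain (points) |
|---|---|---|---|---|
| 4 | 1 | 69.2% | 69.3% | 0.1 |
| 4 | 2 | 69.3% | 71.9% | 2.6 |
| 4 | 4 | 69.2% | 80.0% | 10.8 |
| 12 | 1 | 55.3% | 55.3% | under 0.1 |
| 12 | 3 | 55.4% | 56.7% | 1.3 |
| 12 | 6 | 55.3% | 59.0% | 3.7 |
| 12 | 9 | 55.4% | 62.3% | 6.9 |

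The probability of at least one rejection in the family was identical for the two methods in every row, as it must be, since the first step of Holm is α/m.

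**Secondary check: the threshold under different counts**, at the assumed alpha of 0.05:

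- 4 tests (regions only): 0.05/4 = 0.0125.
- 24 tests (4 regions × 3 modalities × 2 named frequencies): 0.05/24 = 0.0021.
- 200 tests (an assumed count, as might arise at contact level): 0.05/200 = 0.00025.

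A p-value of 0.002 would pass at 4 or 24 tests and fail at 200. I do not attach a power figure to the 200-test case. Moving from a region value to a single contact changes both the effect and its standard error, so one fixed effect size would not give a like-for-like comparison.

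**The case against.** Bonferroni is a legitimate choice that controls the familywise error, so its use is not a mistake. Holm's larger gains need a large share of the comparisons to be real. With 1 real effect in 12 the gain is under 0.1 point, and Holm never changes the chance of obtaining any finding at all. Holm also uses the same number of tests, so by itself it does not close the open family. All of this stands, and it limits the point to a free improvement.

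Three stronger readings are tempting, and the documents do not support them.

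- A reader might infer that the threshold is open over some definite and very large range. No count of contact-level tests appears. Section 2.2.3 describes all implanted contacts, whereas Section 1.3.1 limits the outcome to four regions. The 200-test case, 200/4 = 50 times stricter than 4 tests, is only an illustration.
- A reader might infer that a contact-level correction could put the threshold below the smallest p-value that the rank-sum test can produce. That depends on the number of trials per condition, which the plan does not give. With 8 against 8 trials the smallest exact two-sided p is 2/C(16,8) = 2/12,870 = 0.000155, already below 0.00025, and it falls to 0.000041 at 9 against 9.
- A reader might count random flicker as a further tested frequency and so inflate the family. Section 5 names it as a control, and the primary outcome concerns power at the presented frequency.

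Nor does the plan announce contact-level claims. It is silent on the unit of testing, which is not the same as choosing contacts.

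**Conclusion.** The concern holds in a modest form. Bonferroni in Section 5 is valid but can be improved at no cost in error control. At an assumed two-sided alpha of 0.05 and effects of 3 standard errors, Holm raises average power per real effect from about 55% to 55–62% with 12 tests (1 to 9 real) and from 69% to 72–80% with 4 tests (2 to 4 real). The direction does not depend on these assumptions, but the size does. It shrinks towards zero when few effects are real, and a different effect size or correlation between tests would change it. Since the documents give no effect size, the actual loss under Bonferroni cannot be stated.

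The unfixed number of tests is a secondary gap in specification. It matters because the threshold moves from 0.0125 to 0.0021 on counts taken from the plan's own factors, and to 0.00025 at an assumed 200 tests. It is not evidence that the primary analysis is unworkable.

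**What to change.** In Section 5, replace Bonferroni by Holm for the spectral-power comparisons. In the same place, state the following:

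1. The primary family is the set of region × modality × frequency comparisons against the no-stimulation baseline of Section 1.3.1. Comparisons with random flicker lie outside it.
2. The frequencies in that family are listed in advance, so that the number of tests is fixed.
3. The overall alpha and its sidedness are stated.

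The change of method is one word, and items 1 to 3 take a few sentences. No extra data or procedures are needed. The one technical cost is that Holm has no simple matching simultaneous confidence intervals. Section 5 plans none, and Bonferroni-adjusted intervals could still be shown if wanted.

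The plan should also say how contacts within a region are handled. Averaging them to one value per patient and region is one option, but it dilutes a response confined to a few contacts, so it is the sponsor's choice and not a condition of this change.
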